**Glossary of terms**

Control drug	Drugs(s) used as a comparator to reduce assessment bias, preserve blinding of investigational drug, assess internal study validity, and/or evaluate comparative effects of the investigational drug
Dosage	Dose of the study treatment given to the patient in a time unit (e.g. 100 mg once a day, 75 mg twice a day)
Enrollment	Point/time of patient entry into the study at which study informed consent must be obtained (e.g. prior to starting any of the procedures described in the protocol)
Epoch	A portion of the study which serves a specific purpose. Typical epochs are: screening/recruitment, wash-out, treatment, and follow-up
Investigational drug	The drug whose properties are being tested in the study; this definition is consistent with US CFR 21 Section 312.3 and is synonymous with "investigational new drug" or "investigational medicinal product."
Medication pack number	A unique identifier on the label of each investigational drug package
Patient ID	A unique number assigned to each patient upon signing the informed consent
Randomization number	A unique identifier assigned to each randomized patient, corresponding to a specific treatment arm assignment
Study drug/ treatment	Any single drug or combination of drugs administered to the patient as part of the required study procedures; includes investigational drug (s), placebo/comparator active drug run-ins or background therapy
Study Treatment Discontinuation (TD)	When the patient permanently stops taking study treatment prior to the defined study treatment completion date
Variable	A measured value or assessed response that is determined in specific assessments and used in data analysis to evaluate the drug being tested in the study
Withdrawal of consent	Withdrawal of consent from the study is defined as when a patient does not want to participate in the study any longer, and does not want any further visits or assessments, and does not want any further study related contact, and does not allow analysis of already obtained biologic material

## Amendment 2

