### 3.4 Rationale for choice of comparator

[figure not shown]
A placebo group is included to obtain efficacy, tolerability and safety data in an unbiased manner and to determine the dose-response characteristics of the investigational drug. An active comparator empagliflozin, which is approved in the treatment of T2DM to improve glycemic control, is included as a reference drug ([Zinman et al, 2015](#)). Empagliflozin has also shown CV benefit in T2DM patients in the EMPA-REG Outcome study. Considering that the mechanism leading to the CV benefit with empagliflozin currently remains unclear, the higher of the two approved doses in patients with T2DM, empagliflozin 25mg qd, was chosen as a comparator to potentially achieve a maximum effect on NT-proBNP. Choosing the higher of the two doses should not pose a safety concern, as no difference in the safety profile of empagliflozin 10 mg and 25 mg was reported in the EMPA REG Outcome study in patients with eGFR  $\geq 30$  ml/min/1.73m^2 ([Fitchett et al, 2016](#)), a cut-off value lower than the 45 ml/min/1.73m^2 in CLIK066B2204. In order to minimize potential adverse effects empagliflozin will be up-titrated from 10mg qd to 25mg qd after 2 weeks of treatment.

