To evaluate the effect of all LIK066 doses vs empagliflozin at 12 weeks and 36 weeks on: 
• Change from BL in HbA1c• Change from BL in FPG• Change from BL in weight• Change from BL in body composition (bio-impedance in all patients where appropriate and DXA in a subset of patients)• Change from BL in sitting systolic blood pressure (SBP) and diastolic blood pressure (DBP)• Change from BL in the fasting lipid profile and hs-CRP• Change from BL in 24h urinary glucose and sodium excretion, in a subset of patients	
• Change from BL in HbA1c• Change from BL in FPG• Change from BL in weight• Change from BL in body composition (total body fat mass, visceral fat mass and lean body mass, assessed by bio-impedance)• Change from BL in body composition (total body fat mass, visceral fat level, lean body mass, assessed by DXA, and body water (calculated), in a subset of patients)• Change from BL in SBP and DBP• Percentage change from BL in fasting lipid profile (TG, total cholesterol, HDL cholesterol, LDL cholesterol, calculated VLDL cholesterol and non-HDL cholesterol, lipoproteins (apolipoprotein A-I, apolipoprotein B))• Change from BL in log-transformed hs-CRP• Change from BL in 24h urinary glucose and sodium excretion (in a subset of patients)	Section 2.6.1
To evaluate the change from BL to 36 weeks in all LIK066 doses vs placebo on NT-proBNP	
• Change from BL in log-transformed NT-proBNP at Week 36 (i.e., log-transformed ratio of NT-proBNP (pg/mL) collected at Week 36 to BL)	Section 2.6.1

Objective	Endpoint	Analysis method
To evaluate safety (adverse events (AEs) and lab parameters) and tolerability of LIK066 over 12 weeks and over 36 weeks for all patients	
• Adverse events (AEs)• Deaths• Laboratory data• Vital signs• ECG• Liver events• Renal events	Section 2.6.2
To evaluate 24h urinary calcium and phosphate excretion after 12 weeks and after 36 weeks in a subset of patients	
• Change from BL in 24h urinary calcium and phosphate excretion (in a subset of patients)	Section 2.6.2.8
To evaluate bone mineral density (BMD) in a subset of patients	
• Change from BL in BMD (in a subset of patients)	Section 2.6.2.9

Objective	Endpoint	Analysis method

2 Statistical methods

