2.5.2 Statistical hypothesis, model, and method of analysis

The Multiple Comparison Procedure-Modeling (MCP-MOD) method ([Pinheiro et al, 2006](#) & [Pinheiro et al, 2014](#)) as described in the study protocol will not be performed for the primary endpoint. The following analysis will be performed instead as an exploratory analysis for NT-proBNP. Statistical testing of hypotheses on the endpoint will be performed at the two-sided 0.05 significance level.

The change from baseline in log-transformed NT-proBNP at Week 12 will be analyzed using a mixed effect model of repeated measures (MMRM) in which LVEF at baseline (< 45% vs. \geq 45%), treatment group, visit, and treatment group-by-visit interaction will be included as fixed-effect factors, and baseline log-transformed NT-proBNP will be included as a covariate, with a common unstructured covariance matrix for all treatment groups. The analysis will be performed based on change from baseline in log-transformed NT-proBNP at all post-baseline scheduled visits up to Week 12 and based on likelihood method with an assumption of missing at random (MAR) for missing data. Based on the MMRM model, the estimates and the 95% confidence intervals will be provided for the adjusted means of the change from baseline in log-transformed NT-proBNP at Week 4 and at Week 12 for each treatment group, and for the adjusted mean difference at Week 4 and at Week 12.

The treatment effect (mean difference) of LIK066 doses vs. Placebo or LIK066 doses vs. empagliflozin will be analyzed using the MMRM model as described above including all treatment groups: LIK066 2.5mg qd, LIK066 10gm qd, LIK066 50mg qd, Empagliflozin 25mg qd and Placebo qd. For the comparison of LIK066 doses vs. Placebo, the treatment effects of LIK066 2.5mg qd vs. Placebo qd, LIK066 10mg qd vs. Placebo qd, and LIK066 50mg qd vs. Placebo qd will be presented; For the comparison of LIK066 doses vs. EMPA, the treatment effects of LIK066 2.5mg qd vs. Empagliflozin 25mg qd, LIK066 10gm qd vs. Empagliflozin 25mg qd, and LIK066 50mg qd vs. Empagliflozin 25mg qd will be presented. The analysis results will be back-transformed for ease of data interpretation.

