2.5.4 Supportive analyses

Summary statistics (n, mean, standard deviation (SD), median, Q1, Q3, minimum, maximum, geometric mean and its 95% confidence interval) will be presented by visit and treatment for NT-proBNP and change from BL in NT-proBNP in the double-blind period, for all patients and by baseline LVEF (< 45% vs. \geq 45%). Figures will be produced to visually show the mean changes by visit over 12 weeks of Epoch 3 for each treatment group, for all patients and by LVEF group (< 45% vs. \geq 45% at baseline).

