2.6.1.2 Analysis method

Summary statistics (n, mean, standard deviation, median, Q1, Q3, minimum and maximum) will be provided by visit and treatment for the following variables in the double-blind period, for measurement at each visit and change from baseline values:

- HbA1c

- FPG
- SBP and DBP
- Weight
- Body composition (total body fat mass, visceral fat level and lean body mass, assessed by bio-impedance)
- Body composition (total body fat mass, visceral fat mass, lean body mass, assessed by DXA, and body water (calculated), in a subset of patients)
- 24h urinary glucose and sodium excretion (in a subset of patients)
- Left atrial size and volume assessed by echocardiography

In addition, summary statistics will be provided for left atrial size and volume by baseline LVEF (< 45% vs. \geq 45%).

For the analysis of NT-proBNP, please see details in [Section 2.5](#).

Summary statistics (n, mean, standard deviation, median, Q1, Q3, minimum and maximum) will be provided by visit and treatment for the following variable in the double-blind period, for measurement at each visit and percentage change from baseline values:

- Fasting lipid profile (TG, total cholesterol, HDL cholesterol, LDL cholesterol, calculated VLDL cholesterol and non-HDL cholesterol, lipoproteins (apolipoprotein A-I, apolipoprotein B))

Summary statistics (n, mean, standard deviation, median, Q1, Q3, minimum, maximum, geometric mean and its 95% confidence interval) will be provided by visit and treatment for hs-CRP in the double-blind period, for measurement at each visit and change from baseline values. The change from BL in NYHA class at a given visit is a three-category ordinal variable (improved/unchanged/worsened) with the following definition: 1. Improved, if NYHA class decreases at least one level from BL; 2. Unchanged, if NYHA class is unchanged from BL; 3. Worsened, if NYHA class increases at least one level from BL. NYHA class (I/II/III/IV) will be summarized by visit and treatment group using frequency and percentage. A visit-based shift table will be provided to summarize the NYHA class shifting from BL

All secondary efficacy data will be listed at the individual patient level.

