LIK high dose (n=124) versus placebo (n=124)*	0.5%	1	96%
Any LIK low dose (n=62) versus placebo (n=124)*	0.5%	1	85%

*assuming 10% information loss due to drop-out.

Table 3-3 Comparison of LIK versus empagliflozin

	Expected treatment difference	SD	Probability of the 95% confidence interval upper bound < 0.4%
LIK high dose (n=124) versus EMPA (n=124)	0	1	84%
Any LIK low dose (n=62) versus EMPA (n=124)	0	1	68%

*assuming 10% information loss due to drop-out.

The calculations in Table 3-2 and 3-3 were performed using nQuery 7.0. No multiple testing adjustment was applied.

4 Change to protocol specified analyses

Due to the early termination of the CLIK066B2204 study, the following major changes to the protocol specified analyses have been made in the SAP amendment 1:

- “Week 12 Analysis” and “End of Study Analysis” as defined in the study protocol are no longer applicable. The analyses for the abbreviated CSR will be carried out after the completion of the study.
- MCP-Mod will not be performed for the primary endpoint change in log-transformed NT-proBNP at Week 12. Instead, MMRM will be performed as an exploratory analyses for NT-proBNP. See details in Section 2.5.
- Summary statistics will be provided for selected efficacy endpoints. All efficacy endpoints will be listed. See details in Sections 2.5, 2.6.1.2, 2.7.1.2.
- Subgroup analyses will only be performed for demographics and baseline characteristics, primary and key secondary efficacy endpoints summary statistics, AEs and AEs of special interest, in the subgroups LVEF <45% vs. >= 45%.

5 Appendix

The missing or partially missing AE start/end date and concomitant medication start/end date will be imputed using the Novartis ADaM Governance Board (AGB) global standard approach. Details will be provided in the study Programming Datasets Specifications.

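### Does the exploratory NT-proBNP model in SAP 2.5.2 need a named empagliflozin-versus-placebo contrast?

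*SAP*

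**What the plan says.** SAP Section 2.5.2 drops MCP-Mod because the study ended early and fits one exploratory model to NT-proBNP instead. All five arms enter. The model yields estimates and 95% confidence intervals "for the adjusted means of the change from baseline in log-transformed NT-proBNP at Week 4 and at Week 12 for each treatment group", and also for adjusted mean differences. On those differences the section says: "The treatment effect (mean difference) of LIK066 doses vs. Placebo or LIK066 doses vs. empagliflozin will be analyzed using the MMRM model". It then names the ones to be shown: three LIK066 doses against placebo and the same three against empagliflozin.

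Section 2.5.4 adds descriptive statistics, including "geometric mean and its 95% confidence interval) will be presented by visit and treatment for NT-proBNP and change from BL in NT-proBNP". The other NT-proBNP references lead back to the same place. Section 2.6.1.2 has "For the analysis of NT-proBNP, please see details in" Section 2.5, and Section 4 says "MMRM will be performed as an exploratory analyses for NT-proBNP. See details in Section 2.5".

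The visible NT-proBNP objectives compare LIK066 with placebo. The primary objective does so at Week 12, and the later one in SAP Table 1-1 reads "To evaluate the change from BL to 36 weeks in all LIK066 doses vs placebo on NT-proBNP". Protocol Section 3.4 calls empagliflozin a reference drug and says the 25 mg dose "was chosen as a comparator to potentially achieve a maximum effect on NT-proBNP".

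**The concern.** An active reference arm is often used to show that a trial could have detected an effect. If LIK066 does not separate from placebo on NT-proBNP, one would want to know whether empagliflozin did. If LIK066 and empagliflozin look alike, one would want to know whether both beat placebo or neither did. The six listed contrasts do not answer this directly.

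Two passages seem to give empagliflozin that role. The protocol glossary says a control drug may serve to "assess internal study validity, and/or evaluate comparative effects of the investigational drug", and Section 3.4 links the dose choice to NT-proBNP. Since the visible NT-proBNP objectives name placebo only, SAP 2.5.2 can also look as if it introduced the LIK066-versus-empagliflozin comparison and forgot its companion. If so, a flat LIK066 result could not be told apart from an insensitive trial.

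**Working it through.** **1. Inputs.** Protocol Section 9.8 plans 124 patients each on placebo, LIK066 50 mg and empagliflozin, and 62 on each lower LIK066 dose. The SD of the log ratio is 0.85 (range 0.8 to 0.9). The footnote to Table 9-1 reduces 372 patients (124 + 124 + 62 + 62) to 336 (112 + 112 + 56 + 56). The same 10% loss is assumed here for empagliflozin: 124 × 0.9 ≈ 112.

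**2. The plan's own figure.** Take six optimal contrasts, evaluable sizes 112/56/56/112, a 25% reduction at 50 mg, SD 0.85 and a one-sided 2.5% max-t critical value of 2.189. Average power is 74.8% and minimum power 71.0%, against 75% and 71% in Table 9-1. The inputs are sound.

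**3. Is the contrast asked for?** The visible objectives (Protocol 2.1 and 2.2, SAP Table 1-1) have two families: LIK066 against placebo and LIK066 against empagliflozin. Protocol Section 9.5.1.2 fits its repeated-measures model for the other continuous outcomes to all five arms and presents the same two families, again without empagliflozin against placebo. The list of six in SAP 2.5.2 has the same structure: 3 + 3.

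**4. What the planned output already contains.**
- Per-arm standard error: 0.85/√112 = 0.0803; 95% half-width 1.96 × 0.0803 = 0.157.
- Empagliflozin minus placebo from the two arm means, covariance ignored: √(0.0803² + 0.0803²) = 0.1136.
- The same contrast taken directly: 0.85 × √(2/112) = 0.1136.
- Interval: ratio multiplied or divided by exp(1.96 × 0.1136) = 1.249 (1.233 at SD 0.8; 1.266 at SD 0.9).

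The point estimate is the difference of two reported means. The interval follows from their reported intervals, up to the small covariance that the shared covariates induce. Subtracting the two listed LIK066 50 mg contrasts as if independent would be the wrong route. It gives √2 × 0.1136 = 0.161, about 41% too wide, because both share the 50 mg arm.

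**5. The scenario that seems to show a loss.** Let both drugs truly reduce NT-proBNP by 25% (the documents assume this for LIK066 only), with 112 per arm, SD 0.85 and two-sided 0.05. In 4,000,000 simulated trials, LIK066 50 mg misses significance against placebo in 28.3%. Empagliflozin is significant in 49.1% of those: 0.283 × 0.491 = 0.139, or 14% of all trials (12% at SD 0.8; 15% at SD 0.9).

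These figures do not measure a benefit. LIK066 works in every simulated trial. In the 14%, it misses by chance while empagliflozin does not. Reading the empagliflozin result as proof that the trial was sensitive would point towards LIK066 being inactive, which is false in all of them.

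**The case for a change.** The best case for the extra contrast is practical. It costs one more statement in a model already being fitted. At planned size it would be as precise as LIK066 50 mg against placebo and more precise than the low-dose contrasts that are listed (half-width 0.223 against 0.273). Within-arm changes are not comparisons with placebo. A contrast named in advance cannot be shown or withheld once results are known. If LIK066 were inactive and empagliflozin active, a clear empagliflozin effect would help: the contrast has 72% power for a 25% reduction with 112 per arm.

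It is true that the contrast is not named in the visible text and that a reader wanting its interval must combine two reported means. The rest carries less weight.

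- Both arm means and their intervals are pre-specified, so the information cannot be withheld selectively.
- The 72% belongs to a full-size trial. The model exists because the study stopped early, and the achieved size is not given. For illustration, power for a 25% reduction is 47% with 62 per arm, 26% with 30 and 11% with 10.
- The documents state no established empagliflozin effect on NT-proBNP, so a null result would say nothing about sensitivity.
- The glossary entry is a generic list of possible roles. It assigns none to empagliflozin here, and Section 3.4 speaks only of a potential effect.
- That SAP 2.5.2 introduced the LIK066-versus-empagliflozin comparison cannot be established. The protocol's table of contents shows a redacted entry after the secondary objectives, and SAP Section 2.7.1.2, which Sections 2.1 and 4 cite, is not in the public text.

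**Conclusion.** The concern does not hold. SAP 2.5.2 as written gives valid estimates for the comparisons it sets out to make, and they match the visible objectives and the protocol's pattern for other endpoints. LIK066 is compared with placebo directly. Empagliflozin against placebo can be recovered from the planned arm means with essentially the precision of a direct contrast: a factor of 1.25 (1.23 to 1.27) at 112 per arm and SD 0.85 (0.8 to 0.9). The gain from naming it would be a printed line.

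This rests on the planned sizes, on 10% loss in the empagliflozin arm and on ignoring covariance between adjusted means. Fewer patients would widen the direct and the rebuilt interval alike; 56 per arm, as an illustration, gives a factor of 1.37 for both. The conclusion covers the visible text. If the unseen sections contain the contrast, the question falls away altogether.

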2.5.3 Handling of missing values/censoring/discontinuations

No imputation will be performed for missing NT-proBNP values.

2.5.4 Supportive analyses

Summary statistics (n, mean, standard deviation (SD), median, Q1, Q3, minimum, maximum, geometric mean and its 95% confidence interval) will be presented by visit and treatment for NT-proBNP and change from BL in NT-proBNP in the double-blind period, for all patients and by baseline LVEF (< 45% vs. \geq 45%). Figures will be produced to visually show the mean changes by visit over 12 weeks of Epoch 3 for each treatment group, for all patients and by LVEF group (< 45% vs. \geq 45% at baseline).

2.6 Analysis of secondary objectives

The secondary efficacy variables will be analyzed in the FAS. Statistical testing of hypotheses on the secondary efficacy endpoints will be performed at the two-sided 0.05 significance level without adjustment for multiplicity. Safety variables will be analyzed in the SAF.

2.6.1 Efficacy variables

2.6.1.1 Variables

For the comparison of LIK066 doses vs. placebo *and* LIK066 doses vs. empagliflozin (EMPA) at Week 12 and Week 36:

- Change from BL in HbA1c
- Change from BL in FPG
- Change from BL in SBP and DBP
- Change from BL in weight
- Change from BL in body composition (total body fat mass, visceral fat mass and lean body mass, assessed by bio-impedance)
- Change from BL in body composition (total body fat mass, visceral fat level, lean body mass, assessed by DXA, and body water (calculated), in a subset of patients)
- Percentage change from BL in fasting lipid profile (TG, total cholesterol, HDL cholesterol, LDL cholesterol, calculated VLDL cholesterol and non-HDL cholesterol, lipoproteins (apolipoprotein A-I, apolipoprotein B))
- Change from BL in log-transformed hs-CRP
- Change from BL in 24h urinary glucose and sodium excretion (in a subset of patients)

For the comparison of LIK066 doses vs. placebo at Week 12 and Week 36:

- Change from BL in left atrial size and volume assessed by echocardiography
- Change from BL in NYHA class

For the comparison of LIK066 doses vs. placebo at Week 36:

- Change from BL in log-transformed NT-proBNP

2.6.1.2 Analysis method

Summary statistics (n, mean, standard deviation, median, Q1, Q3, minimum and maximum) will be provided by visit and treatment for the following variables in the double-blind period, for measurement at each visit and change from baseline values:

- HbA1c

- FPG
- SBP and DBP
- Weight
- Body composition (total body fat mass, visceral fat level and lean body mass, assessed by bio-impedance)
- Body composition (total body fat mass, visceral fat mass, lean body mass, assessed by DXA, and body water (calculated), in a subset of patients)
- 24h urinary glucose and sodium excretion (in a subset of patients)
- Left atrial size and volume assessed by echocardiography

In addition, summary statistics will be provided for left atrial size and volume by baseline LVEF (< 45% vs. \geq 45%).

For the analysis of NT-proBNP, please see details in [Section 2.5](#).

Summary statistics (n, mean, standard deviation, median, Q1, Q3, minimum and maximum) will be provided by visit and treatment for the following variable in the double-blind period, for measurement at each visit and percentage change from baseline values:

- Fasting lipid profile (TG, total cholesterol, HDL cholesterol, LDL cholesterol, calculated VLDL cholesterol and non-HDL cholesterol, lipoproteins (apolipoprotein A-I, apolipoprotein B))

Summary statistics (n, mean, standard deviation, median, Q1, Q3, minimum, maximum, geometric mean and its 95% confidence interval) will be provided by visit and treatment for hs-CRP in the double-blind period, for measurement at each visit and change from baseline values. The change from BL in NYHA class at a given visit is a three-category ordinal variable (improved/unchanged/worsened) with the following definition: 1. Improved, if NYHA class decreases at least one level from BL; 2. Unchanged, if NYHA class is unchanged from BL; 3. Worsened, if NYHA class increases at least one level from BL. NYHA class (I/II/III/IV) will be summarized by visit and treatment group using frequency and percentage. A visit-based shift table will be provided to summarize the NYHA class shifting from BL

All secondary efficacy data will be listed at the individual patient level.

